### 5.2.5. Vaso-occlusive Crisis (VOC)

An on-study sickle cell-related VOC is defined as an acute episode of new-onset pain that lasts at least 2 hours with no medically determined cause other than a vaso-occlusive event and that requires treatment with oral or parenteral opioids, or parenteral nonsteroidal anti-inflammatory drugs, or other analgesics prescribed by a healthcare provider in a medical facility or by telephone management documented in medical records.

## 5.3. Missing Data

For the purposes of assessing treatment emergence for AEs or classifying medications into prior/concomitant, the following algorithms will be used for partially missing dates. However, the assessment times (start date, stop date) without imputation will be presented in the listings.

For start dates of events:

- Only the year is reported: if the participant received the first dose of randomized study drug in the reported year, date of first dose of randomized study drug will be used as the start date; otherwise '1 January' will be used as the start date.
- Only the month and year are reported: if the participant received the first dose of randomized study drug in the reported month and year, the date of first dose of randomized study drug will be used as the start date; otherwise, the first day of the reported month and year will be used as the start date.

For stop dates of events:

- Only the year is reported: if the last visit is in the reported year, the date of last visit will be used as the stop date; otherwise, '31 December' will be used as the stop date.

This document is confidential.

- Only the month and year are reported: if the last visit is in the reported month and year, the date of last visit will be used as the stop date; otherwise, the last day of the reported month and year will be used as the stop date.

If an AE has the start date completely missing, this AE will be considered as treatment-emergent, unless the stop date is before first dose of randomized study drug.

If a medication has the stop date completely missing, this medication will be considered as ongoing and concomitant.

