### 5.2.4. TEAE, SAE, On-therapy SAE

TEAEs are defined as AEs with a reported started date/time that is on/after the first dose date/time the participant receives randomized treatment through 7 days after the last dose of study medication.

SAEs are AEs that result in death, are life-threatening, require hospitalization or prolongation of existing hospitalization, are persistent or result in significant disability/incapacity, result in a congenital anomaly/birth defect, or are important medical events (eg, events that may not result in death, are life threatening, or require hospitalization; such events may be considered serious when, based on appropriate medical judgment, it may jeopardize the participant and may require medical or surgical intervention to prevent 1 of the outcomes listed in the wider SAE definition).

On-therapy SAEs are those SAEs that start after the participant has received the first dose of randomized study drug and through 28 days after the final study drug dose.

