### 7.2. Adverse Events

AEs will be coded using the MedDRA Version 20.0 or later and will be classified by MedDRA SOC and PT.

AEs are collected from date of signed informed consent form (ICF) through the last Follow-up Visit. TEAEs, SAEs, and on-therapy SAEs are defined in [Section 5.2.4](#). Pre-treatment AEs during Screening are defined as AEs started on/after Screening Visit and before the first dose of Run-in placebo. Pre-treatment AEs during Single-blind Run-in Period are defined as AEs started on/after the first dose of Run-in placebo and before the first dose of randomized study drug.

The number and percentage of participants who experience at least 1 TEAE as well as those who experience each specific SOC and PT will be presented by treatment group for the Safety Population. For presentation of AE incidence, AEs will be sorted by SOC, and within each SOC, by PT in the decreasing incidence of the last column of summary table, and then the column before it one by one. AEs will also be presented by severity (CTCAE v.4.03; Grade 1–Grade 5). For AEs that change severity ratings, the AE will be included only once in the summaries, under the maximum severity rating assigned by the Investigator. Additionally, TEAEs and SAEs occurring in the first, second, and fifth week of the double-

This document is confidential.

blind Treatment Period will be listed separately to distinguish among any effects of the initial dose (Week 1), the up-titrated dose (Week 2), and the further up-titrated dose (Week 5).

AEs occurring during Screening and the Single-blind Run-in Period will be summarized and listed separately.

More specifically, the following summary tables will be provided:

1. Overall Summary of TEAEs
2. Incidence of TEAEs by SOC and PT
3. Incidence of TEAEs by SOC, PT, and severity
4. Incidence of TEAEs by SOC, PT and relationship to double-blind study drug
5. Incidence of on-therapy SAEs by PT
6. Incidence of AEs leading to study drug discontinuation by PT
7. Incidence of pre-treatment AEs during Screening by SOC and PT (Screened Population)
8. Incidence of pre-treatment AEs during Single-blind Run-in Period by SOC and PT (Single-blind Run-in Population)
9. Incidence of adverse events of special interest (AESIs) by PT
10. Incidence of TEAEs by SOC, PT, and region (US vs. Lebanon)
11. Incidence of VOCs by PT
12. Summary of VOC events by location (eg, extremity) and outcome (eg, acute chest syndrome)

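### SAP 5.3 moves partial AE start dates to the first randomized dose without checking the stop date, so an AE shown to have ended before that dose is counted as treatment-emergent

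*SAP*

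**What the plan says.** SAP 5.3 (Missing Data) gives the purpose of its date rules: "For the purposes of assessing treatment emergence for AEs or classifying medications into prior/concomitant, the following algorithms will be used for partially missing dates".

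There are two rules for a partial start date, one for year only and one for month and year. Each asks a single question: did randomized dosing begin in the reported period? If so, "the date of first dose of randomized study drug will be used as the start date" (the year-only rule has the same effect). If not, the first day of the period is used. Neither rule mentions the stop date.

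A separate sentence covers a start date that is completely missing: "this AE will be considered as treatment-emergent, unless the stop date is before first dose of randomized study drug".

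SAP 5.2.4 defines TEAEs by start alone: "AEs with a reported started date/time that is on/after the first dose date/time the participant receives randomized treatment through 7 days after the last dose". SAP 7.2 confirms that pre-randomization events are in the database: "AEs are collected from date of signed informed consent form (ICF) through the last Follow-up Visit". It assigns AEs starting before the first randomized dose to separate Screening and Run-in tables. SAP 3.1 (Table 1) makes the incidence and frequency of TEAEs the primary endpoint.

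**The concern.** The SAP accepts that a stop date before the first randomized dose rules out treatment emergence, but applies this only where nothing is known about the start. Where the month or year is known, the same evidence is ignored. The imputed start then falls after the recorded stop, and nothing in SAP 5.2.4 corrects the result. More information about the date gives a worse classification than none.

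The primary endpoint is at stake. An affected event leaves the pre-treatment tables and enters the TEAE tables. If the imputed date is also used to select events for the first-week listing in SAP 7.2, the event would appear there as an apparent early effect of the initial dose.

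**Working it through.** The documents state no figure that depends on this rule, and the sample size was not set statistically (SAP 3.4), so there is no plan figure to reproduce. The check applies the rules literally.

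**Step 1. One AE at four levels of start-date completeness.** Assumed dates: first randomized dose 20 March 2019, AE stop 12 March 2019. An imputed date equal to the first-dose date is taken as on or after first dose.

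| Start as recorded | Start used | TEAE under SAP 5.3 | TEAE with a stop-date check |
|---|---|---|---|
| 10 March 2019 | 10 March 2019 | no | no |
| March 2019 | 20 March 2019 | yes | no |
| 2019 | 20 March 2019 | yes | no |
| missing | none | no | no |

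In the two middle rows the AE starts 20 − 12 = 8 days after it ended.

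**Step 2. Share of susceptible AEs affected.** The set is AEs that started in the run-in, ended before Day 1 and have a partial start date. The run-in lasts R = 14 to 17 days (Protocol 3.1). Assume that Day 1 is equally likely on any day of a 30-day month and that AE starts are spread evenly over the run-in. An AE starting L days before Day 1 falls in the same month with probability (30 − L)/30, and L averages (R + 1)/2.

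- R = 14: (30 − 7.5)/30 = 75%
- R = 17: (30 − 9)/30 = 70%

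Running every Day 1 date in calendar 2019 (an assumed year) against every run-in day gives 75.3% and 70.4%.

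With year only, the AE escapes only if it began in the previous calendar year. That is R(R + 1)/2 of the 365R combinations:

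- R = 14: 105/5110 = 2.1%, so 97.9% are misclassified
- R = 17: 153/6205 = 2.5%, so 97.5% are misclassified

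With the stop-date check added, the count is 0 in every enumerated case.

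The even spread is an assumption. AEs that have resolved by Day 1 may have begun earlier in the run-in on average, which lowers the month-and-year share. For an AE starting on the first run-in day it is (30 − 14)/30 = 53% or (30 − 17)/30 = 43%.

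**Step 3. Effect of one participant.** Planned arm sizes (SAP 3.2 and 3.4) are 40/4 = 10 per Amendment 3 arm. From Amendment 4 they are 48 × 3/4 = 36 on 18 mg and 48 × 1/4 = 12 on placebo. Overall placebo is 10 + 12 = 22. The most that one participant can add to overall TEAE incidence is 100/n:

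- n = 10: 10 points
- n = 12: 8.3 points
- n = 22: 4.5 points
- n = 36: 2.8 points

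Incidence counts participants with at least one TEAE. The increment is therefore reached only if the participant has no other TEAE up to 7 days after last dose. Otherwise overall incidence is unchanged, and the error shows in the SOC/PT row (if the participant is not already counted there) and as one extra event in the frequency count.

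**The case against.** **The trigger is narrow.** It needs a partial start date in the first-dose month or year and a stop date good enough to show the AE ended before Day 1. AEs are evaluated at the Run-in and Randomization Visits (Schedule of Events), monitors raise missing data with the Investigator (Protocol 7.1), and missing data should be explained (Protocol 7.3). This stands: the number may be small.

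**Imputing to first dose is the usual conservative choice.** That is right when the stop date is missing or falls on or after Day 1. It is no defence when the stop date settles the matter. A reader might infer that 70 to 75% of all run-in AEs with a missing start day are misclassified. The documents do not support that, because the share covers only AEs shown to have ended before Day 1.

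**The comparison is not biased.** A reader might infer that the rule attributes events to olinciguat. It does not. TEAE is a timing label, and relatedness is a separate Investigator judgement (Protocol 3.8.8.3). The affected events precede randomized treatment, so misclassification should be equal in expectation across concurrently randomized arms, placebo included. This stands, although chance imbalance is possible in arms of 10 to 36.

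**The error would be visible.** Listings show unimputed dates (SAP 5.3) and all AEs are listed (SAP 7.2). That is true, but the primary endpoint is tabulated from the classification.

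**The TEAE definition refers to the reported start.** This could be read as excluding imputed dates. SAP 5.3 says that its algorithm serves to assess treatment emergence, so that reading fails.

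**Conclusion.** The rule is wrong as written. For an AE with a partial start date in the first-dose period and a stop date before first dose, SAP 5.3 gives a demonstrably false classification and contradicts its own treatment of a missing start date.

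The size is conditional. Within the susceptible run-in set, about 70 to 75% are misclassified with month and year known and about 98% with year only, on the assumptions in the working. How many AEs make up that set cannot be determined from the documents. The point increments are maxima for one participant, and a reader should not take them as the expected effect. The likely result is some inflation of TEAE rates in every arm, with no expected advantage to either treatment. That is worth correcting because the endpoint is primary and the correction is easy; it does not threaten the trial's conclusions.

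**What to change.** Add one condition to both partial-start rules in SAP 5.3:

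*If the stop date, complete or as imputed by the stop-date rules of this section, is before the first randomized dose, the AE is not treatment-emergent. Its imputed start is then the earliest date consistent with the partial date, but not before the Screening Visit and never after the stop date.*

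The second sentence is needed because SAP 7.2 places pre-treatment AEs in the Screening or Run-in table by start date. It is a tabulation convention: some run-in events may land in the Screening table, but the TEAE count is unaffected.

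Using the existing stop-date rules keeps the approach conservative. A partial stop date is imputed to the end of its period or to the last visit, so it precedes first dose only when the whole reported period does. AEs with a missing stop date, or one not shown to precede first dose, remain treatment-emergent.

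The cost is a short text change and one extra condition in the AE derivation, with no new data, before database lock. If the AE tables have already been produced, they should be rerun and the number of reclassified AEs reported by arm.

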#### 5.4. Visit Windows

The following algorithms will be used to map the analysis visit for the on-treatment analysis.

Analysis Visit	Mapping Window (Study Day)
Week 1	Day 7 to Day 14
Week 4	Day 15 to Day 36
Week 8	Day 37 to Day 64
Week 12	Day 65 to (last dosing date + 4 days)

End of Treatment (EOT) analysis visit is defined as the last measurement taken that is on-treatment. For all endpoints other than TEAEs, 'on-treatment' is defined as the first dosing date through 4 days after the end of treatment visit (the last dosing date + 4 days).

Last dosing date needs to be considered for all mappings. eg, if participant comes in for Week 8 but is more than 4 days out of last dosing, then that visit will not be mapped to Week 8 for analysis as the participant is not 'on-treatment'.

If multiple measures are mapped to same analysis visit, the last set of records will be included in the analysis. In listings, data will be presented with visit collected, analysis visit mapped, and analysis flag.

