- Run-in Period:** The single-blind Run-in will begin at least 3 days after the Screening Visit and is defined as the 14 to 17 days before the first dose of double-blind study drug on Day 1. At the Run-in Visit, eligible patients will take their first single-blind (placebo) dose in the clinic, will undergo safety and pharmacodynamic (PD) assessments, and will complete patient-reported outcome (PRO) questionnaires in an eDiary (a handheld personal electronic device) that will be issued for their use. They will continue to take once-daily single-blind placebo at home and will record daily and weekly assessments in their eDiary throughout this period. Patients will be required to complete at least 10 days of daily assessments during the final 14 days of the Run-in Period to remain eligible for randomization into the Treatment Period.

Treatment Period: The double-blind Treatment Period will begin on Day 1 at Randomization (there is no Day 0) and will end after the End-of-Treatment (EOT) Visit on Day 85 (-7/+4).

Eligible patients will take their first dose of double-blind study drug in the clinic on Day 1 and will undergo safety, PRO, PK, and PD assessments at prespecified times according to the [Schedule of Events](#). Patients must remain in the clinic at least 6 hours postdose and thereafter will be allowed to leave at the Investigator's discretion. Starting on Day 2, patients will take their daily double-blind study drug dose at home, per Section [3.5.4.1](#). Also on Day 2, preferably in the afternoon, patients will receive a phone call for adverse event (AE) and concomitant medication and procedure(s) assessment. Throughout the Treatment Period, patients will continue to record daily assessments in their eDiary.

At their Week 1 (Day 8 [± 1]) and Week 4 (Day 29 [± 3]) visits, respectively, patients who meet the uptitration criteria (see Section [3.5.4.2](#)) will begin taking the applicable higher dose. At these visits, patients must again stay in the clinic at least 6 hours postdose to undergo safety, PRO, PK, and PD assessments at prespecified times according to the [Schedule of Events](#) and thereafter will be allowed to leave at the Investigator's discretion. On the day after these 3 visits, preferably in the afternoon, patients will receive a phone call for assessment of AEs and concomitant medication(s) and procedure(s).

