3.4.3 Early Termination Procedures

Patients who prematurely discontinue study drug for any reason should complete the safety and PRO assessments that are required at the End of Treatment Visit at the time of their discontinuation and should return to complete the Follow-up Visit 28 -3/+7 days after their final dose of study drug. In addition, for patients who discontinue ≥ 4 weeks post randomization and have specifically consented to participate in a cognitive debriefing interview, the site will notify the third-party vendor of the date of the patient's Early Termination Visit and their contact information; see Section 3.8.9.4.

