3.5.1.4 Dosing Regimens

Table 1 summarizes the dosing regimen for all patients during the Run-in Period. Patients will be masked to their treatment (single-blind dosing; see Section 3.5.6).

Table 1. Dose Regimen During Single-blind Run-in Period

Dosage	Run-in (Day -17 or -14 to Day -1); QD Dose
placebo daily	1×matching placebo tablet
QD=once daily	

On Day 1 of the Treatment Period, patients will be randomized to double-blind study drug in a 3:1 ratio (IW-1701:placebo). [Table 2](#) summarizes the dosing scheme for each treatment arm by Treatment Period week.

Table 2. Dosing Scheme, by Double-blind Treatment Period Week

Initial Dose Level (Day 1–Day 7)		Week 1 through Week 3 (Day 8–Day 28)		Week 4 through Week 12 (Day 29–Day 85)	
QD Dose	QD Dosage	QD Dose	QD Dosage	QD Dose	QD Dosage
6 mg IW-1701 daily	2×3-mg IW-1701 tablet	12 mg IW-1701 daily	4×3-mg IW-1701 tablet	18 mg IW-1701 daily	6×3-mg IW-1701 tablet
PBO daily	2×matching PBO tablet	PBO daily	4×matching PBO tablet	PBO daily	6×matching PBO tablet

Note: Patients must meet criteria in Section [3.5.4.2](#) to uptitrate.

PBO=placebo; QD=once daily

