### **7.3. Laboratory Evaluations**

Clinical laboratory parameters (chemistry, hematology, urinalysis) will be summarized as outlined in Table 7. Baseline is defined as the last non-missing measurement before administration of study treatment on Day 1 of the Double-blind Treatment Period. If there is more than 1 measurement for a laboratory parameter at a post-baseline time point, only the last measurement will be used. A listing of clinically significant clinical laboratory abnormalities will be presented. All lab data will be listed.

This document is confidential.

Table 7. Clinical Laboratory Summaries

Endpoint	Description	Timing	Summary Method
CTCAE v4.03 grading for laboratory values (Grades $\geq 3$ )	Summarized by laboratory parameter and CTCAE grade	First dose of study drug through last laboratory measure	Categorical summary
Descriptive	Summary of laboratory parameter (SI Units) at each timepoint measured plus change from baseline	Baseline, Week 1, Week 4, 8, 12 (EOT)	Continuous summary

CTCAE=Common Terminology Criteria for Adverse Events; SI=international system [of]; EOT=end of treatment.

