### 8.1. Hemodynamics

The hemodynamic parameters are listed here:

- Change from Day 1 baseline in seated systolic and diastolic blood pressures (BPs) and pulse to predose at Weeks 1, 4, 8, and 12
- Change from Day 1 baseline in orthostatic systolic and diastolic BPs and pulse to predose at Weeks 1, 4, 8 and 12
- For each study visit (Day 1, Weeks 1, 4, 8, 12), change from predose to each postdose time point of the same visit for seated systolic BP, diastolic BP and pulse.

Details about BPs and pulse assessment are included in [Section 7.4](#). An orthostatic measurement is derived by subtracting the seated measurement from the standing measurement.

Descriptive statistics will be tabulated for each hemodynamic parameter by treatment group. In addition, an analysis of covariance (ANCOVA) model will be fitted with change from baseline as dependent variable, treatment group, and stratification factor (HU use) as fixed effects, and corresponding baseline value as covariate, at each visit/time point. Pairwise contrasts will be used to compare each olinciguat group with the placebo group. Least-squares means (LSMs) for each treatment group, LSM differences between each olinciguat group and the placebo group, their corresponding 2-sided 95% CIs, and p-values will be presented. Example SAS code for ANCOVA model is shown below:

```
Proc mixed data = analysis_data;
  class stratum trt;
  model chg = base stratum trt;
  lsmeans trt/ cl diff;
run;
```

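### SAP 5.4 keeps the last record in visit windows that run past the dose steps, so an early-termination reading can replace the scheduled Week 1 or Week 4 value

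*SAP*

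**What the plan says.** SAP 5.4 maps on-treatment records by study day. Week 1 is Days 7 to 14 and Week 4 is "Day 15 to Day 36". A record counts as on-treatment up to 4 days after the last dose. Where a window holds more than one record, the rule is: "If multiple measures are mapped to same analysis visit, the last set of records will be included in the analysis". SAP 7.3 has a parallel rule for laboratory data: "If there is more than 1 measurement for a laboratory parameter at a post-baseline time point, only the last measurement will be used". Neither section gives priority to the nominal visit, closes a window at a dose step, or says how early-termination records are mapped.

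The dose steps fall inside these two windows. Protocol 3.1 reads: "At their Week 1 (Day 8 [± 1]) and Week 4 (Day 29 [± 3]) visits, respectively, patients who meet the uptitration criteria" will begin the higher dose. Protocol 3.5.4.1 places the in-clinic dose after the predose assessments, so that these are taken at trough. The hemodynamic endpoints in SAP 8.1 rely on this: "Change from Day 1 baseline in seated systolic and diastolic blood pressures (BPs) and pulse to predose at Weeks 1, 4, 8, and 12".

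Under Protocol 3.4.3, patients who stop study drug early "should complete the safety and PRO assessments that are required at the End of Treatment Visit at the time of their discontinuation".

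**The concern.** The scheduled laboratory and trough vital-sign readings at the Week 1 and Week 4 Visits describe the dose taken before the step. PROMIS and ASCQ-Me are completed within an hour after dosing. PROMIS looks back over 7 days, so its scheduled record also describes mainly the pre-step dose.

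A patient who steps up and then stops outright attends a required early-termination visit. If that visit still falls in the window and is on-treatment, it is the last record there and the scheduled one is set aside. For that patient, the labelled visit now follows dosing at the higher level, or up to 4 days off drug. Patients who stay on drug contribute the reading taken at the step visit.

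The SAP treats the steps as important elsewhere. Section 7.2 lists adverse events in Weeks 1, 2 and 5 separately to tell the dose levels apart. The last-record rule blurs that separation for by-visit laboratory, vital-sign and visit-questionnaire results. It also discards a valid scheduled value without need, because the EOT analysis visit already captures the termination record.

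**Working it through.** The documents give no power calculation, effect size or dropout rate, so there is no plan figure to reproduce. The check maps study days through the windows.

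**Inputs**
- Windows: Week 1 = Days 7–14, Week 4 = Days 15–36, Week 8 = Days 37–64, Week 12 = Day 65 to last dose + 4 (SAP 5.4).
- Scheduled visits: Day 8 ±1, Day 29 ±3, Day 57 ±7, Day 85 −7/+4 (Schedule of Events).
- Steps: at the Week 1 and Week 4 Visits under Amendment 4 or later (Protocol 3.1). Under Amendment 3 or earlier there is one step, after Week 1 (SAP 3.5).
- Arm sizes: about 48 patients at 3:1 gives 48 × 3/4 = 36 on 18 mg and 48 × 1/4 = 12 on placebo. About 40 at 1:1:1:1 gives 40 × 3/4 = 30 on active drug under the earlier amendments.
- Assumption: dropout of 5% to 30%, spread evenly over Days 2–85 (84 days).

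**Step 1. What the rule acts on.** Scheduled visits fall on Days 7–9, 26–32, 50–64 and 78–89, each alone in its own window. SAP 5.1 keeps unscheduled and repeat readings out of summary tables. The last-record rule therefore acts mainly on early-termination visits, or on visits held outside tolerance.

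**Step 2. Days open after the step** (window end minus visit day)
- Week 1: 14 − 9 = 5 to 14 − 7 = 7 days; 14 − 8 = 6 for an on-target visit.
- Week 4: 36 − 32 = 4 to 36 − 26 = 10 days; 36 − 29 = 7 for an on-target visit.

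**Step 3. Examples**
- Last dose Day 12, termination visit Day 13: on-treatment (limit 12 + 4 = 16), mapped to Week 1, replaces the Day 8 record.
- Last dose Day 32, termination visit Day 34: on-treatment (limit 32 + 4 = 36), mapped to Week 4, replaces the Day 29 record.
- Last dose Day 32, termination visit Day 37: past the limit, so no replacement.

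**Step 4. Reach**
- Affected: laboratory values, including the Hb and HbF ANCOVA, MMRM and responder summaries (SAP 7.3, 8.3); vital-sign summaries (SAP 7.4); PROMIS and ASCQ-Me (SAP 8.4.2, 8.4.3). This holds in the Safety or ITT set, as applicable.
- Conditional: the hemodynamic endpoints, only if a termination reading is labelled predose. The SAP does not say.
- Not affected: TEAEs (own definition, SAP 5.2.4); ECG (none scheduled at EOT); SCD-SAF and analgesic use (own 7-day diary weeks).
- Not affected: the Evaluable Population. It needs at least 6 weeks of drug (SAP 4.6), that is 42 days, and 42 > 36.

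**Step 5. Expected number.** For Amendment 4 or later with on-target visits, expected cases = n × dropout × (6 + 7)/84 = n × dropout × 0.155. The chance of at least one case is 1 − (1 − dropout × 0.155)^36.

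| Assumed dropout | 18 mg (n = 36) | Placebo (n = 12) | Chance of ≥1 on 18 mg |
|---|---|---|---|
| 5% | 0.28 | 0.09 | 24% |
| 10% | 0.56 | 0.19 | 43% |
| 20% | 1.11 | 0.37 | 68% |
| 30% | 1.67 | 0.56 | 82% |

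For the earlier amendments only Week 1 counts: 30 × dropout × 6/84 = 0.11 at 5% to 0.64 at 30%.

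**Step 6. Effect of one case.** One record is 1/36 = 2.8% of the arm. If it differs from the scheduled value by one SD, the arm mean moves by SD/36. The standard error of the unadjusted 36-versus-12 difference is SD × √(1/36 + 1/12) = SD/3. The shift is therefore (1/36)/(1/3) = 1/12, or about 8% of one standard error.

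**The case against.** The strongest reply is that few patients can be caught. Under Protocol 3.5.4.3, a patient who does not tolerate 12 or 18 mg is to go back to the prior tolerated level, not to stop, and so continues to the next scheduled visit. A clinic evaluation before such a reduction is off schedule, and SAP 5.1 keeps it out of the tables. Only patients who stop outright soon after a step remain. The planned Evaluable analyses exclude all of them, the affected analyses are exploratory, and the SAP 5.4 listings show the visit collected, the visit mapped and the analysis flag. All of this stands and limits the size of the problem.

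It could also be said that SAP 5.1 already removes termination records as unscheduled. That is not clear. The visit is required by the protocol and is not named in SAP 5.1, and the EOT definition needs such records.

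A reader might infer several stronger things that the documents do not support:
- *The effect falls mainly on active drug.* Beyond the 3:1 allocation, nothing in the documents shows this.
- *The termination record is wrongly counted twice.* EOT is defined as the last on-treatment measurement, so a completer's Week 12 record is also EOT. The two are separate displays.
- *Every other patient's Week 4 value is a trough on 12 mg.* Results are grouped by randomized regimen, and Protocol 3.5.4.2 and 3.5.4.3 let patients in the 18 mg arm be on a lower level by then.
- *The blood-pressure models are certainly distorted.* Those endpoints are defined as predose, and a reading at a visit without dosing may not qualify. Laboratory values are the clearest case.

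**Conclusion.** The concern holds in limited form. As written, SAP 5.4 lets a protocol-required early-termination assessment displace a valid scheduled Week 1 or Week 4 record, and SAP 7.3 says the same for laboratory data. The Week 1 part can occur under any amendment; the Week 4 part only under Amendment 4 or later.

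The likely size is about 0.3 to 1.7 of 36 patients on 18 mg. This rests on the assumed 5–30% dropout, even spread and on-target visits. Requiring the visit to fall within 4 days of the last dose would lower the count; clustering of stops after a step would raise it. Each case moves a by-visit mean only slightly. No primary endpoint changes, and the trial's main conclusions are not in question. The change is still worth making, because the rule discards the correct by-visit value in patients selected by stopping early, and correcting it costs almost nothing.

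**What to change.** Before database lock, replace the last-record sentence in SAP 5.4 and bring SAP 7.3 into line:

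- Use the record from the scheduled nominal visit when one exists in the window.
- Otherwise use the on-treatment record closest to the target day (8, 29, 57 or 85). For predose (trough) endpoints, use only a record taken before the next dose level starts.
- Map early-termination records to EOT, and to a numbered week only when that window has no scheduled record.

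Closeness to the target day should stay the fallback and not become the main rule. With a Week 4 Visit on Day 26 and a termination visit on Day 30, the termination record is nearer to Day 29 (1 day against 3) and would still displace the scheduled one.

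If the intention is already that termination records feed EOT only, the SAP should say so. The cost is one SAP sentence, the matching edit in 7.3 and a change to the visit-mapping program. No new data are needed.
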